#### **14.7 Interim Efficacy Assessment and Interim Analyses**

An interim efficacy assessment will be performed after the first 14 patients are enrolled and have completed step one. Progression events will be the primary concern for the interim efficacy analysis. Progression, as used for this purpose, will be defined as disease progression on CT scan of the neck (assessed by RECIST criteria) occurring at the completion of step one. The occurrence of three or more progression events during step one will be cause to stop trial accrual to assess if the trial should be amended, closed, or continued as planned. The interim analysis will be prepared for preliminary (abstract) presentation at cancer meeting(s). Trial accrual will not be stopped while the interim efficacy analysis is ongoing. The stopping rule will not be considered in this interim efficacy analysis given the small sample size.

A safety assessment will be performed for the first 14 patients enrolled using a continuous method. The safety endpoint of interest is delays in starting potentially curative chemoradiation therapy defined as failure to start chemoradiation within three weeks of cycle 2 day 28 (of Step One) due to adverse events considered to be definitely, probably, or possibly related to palbociclib. Trial accrual should be stopped to assess if the trial should be amended, closed, or continued as planned, using the following thresholds for continuous assessment:

# of patients delayed in starting chemoradiation	In first # of patients
2	4
2	5
2	6
3	7
3	8
3	9
4	10
4	11
4	12
4	13
5	14

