### **5.0 TREATMENT PLAN**

“The three step” trial is a two cohort, non-randomized phase II trial in which palbociclib will be integrated into the standard CRT regimen with either cisplatin (cohort 1) or cetuximab (cohort 2). Patients with stage III-IV (non-metastatic) p16INK4a negative, HPV-unrelated HNSCC will be enrolled, to enrich the fraction of patients most likely to benefit from a CDK4/6 inhibitor.

During step one, patients in both cohorts will be treated with neoadjuvant palbociclib monotherapy (125 mg/day, Days 1-21 of a 28-day cycle for two cycles). A CT scan of the neck to assess tumor response and a tumor biopsy for pharmacodynamics assessment will be performed before and after palbociclib (CT scan – Cycle 2 post-treatment Day 21 through Day 25; Tumor biopsy Cycle 2 Day 21). Data will be pooled from the two cohorts to address the primary aim. The primary aim of the trial is to determine the tumor response rate (using RECIST 1.1) of newly diagnosed p16INK4a negative, HPV-unrelated HNSCC to palbociclib monotherapy given over two cycles, and to explore potential pharmacodynamic determinants of tumor response to palbociclib monotherapy using data derived from genomic, RNA, and protein expression methods performed on pre- and post-treatment tumor tissue.

During step two (CRT), Cohort 1 patients will be treated with cisplatin 100 mg/m^2 given on Days 1 and 22 with RT. Cohort 2 patients will be treated with cetuximab given one week before RT and then weekly during RT. Cohorts 1 and 2 will receive accelerated IMRT 70 Gy to be administered over 6 weeks in once daily fractions Monday through Friday, with one additional fraction of RT administered on (preferably) Fridays. The two fractions administered on one day will be at least 6 hours apart. Palbociclib, an oral agent, will not be given during step two due to the severe difficulty with swallowing that occurs in all patients treated with CRT and due to the lack of feasibility

studies for this combination therapy. To assess overall tumor response (stratified by cohort), a CT scan of the neck will be performed 8-10 weeks following completion of CRT, and FDG-PET/CT will be performed 14-18 weeks following completion of CRT.

During step three, patients in both cohorts will be treated with adjuvant palbociclib 125 mg/day, days 1-21 of each 28-day cycle for six cycles. Adjuvant palbociclib will begin 16 to 22 weeks following completion of CRT.

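### Section 14.7 schedules the three-progression check once, after 14 patients complete Step One; if the trigger is kept it should run as a count, because the third progression already settles it

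*Combined protocol and SAP*

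**What the plan says.** The efficacy paragraph of section 14.7 (Interim Efficacy Assessment and Interim Analyses) contains five statements that bear on timing.

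- The look: "An interim efficacy assessment will be performed after the first 14 patients are enrolled and have completed step one".
- The event: "disease progression on CT scan of the neck (assessed by RECIST criteria) occurring at the completion of step one".
- The trigger: "The occurrence of three or more progression events during step one will be cause to stop trial accrual", after which the trial may be amended, closed or continued as planned. This sentence gives no date and no denominator.
- Accrual: "Trial accrual will not be stopped while the interim efficacy analysis is ongoing".
- The closing sentence: "The stopping rule will not be considered in this interim efficacy analysis given the small sample size".

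The next paragraph treats delayed chemoradiation differently: "A safety assessment will be performed for the first 14 patients enrolled using a continuous method". It has a table of running thresholds. Progression has no such wording and no table.

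Section 5.0 gives Step One as palbociclib on "Days 1-21 of a 28-day cycle for two cycles", which is 2 × 28 = 56 days. Sections 5.3.3 and 5.3.4 start Step Two the day after Cycle 2 Day 28. Section 14.7 itself describes the chemoradiation as potentially curative.

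**The concern.** The trigger is a cumulative count, and a cumulative count cannot fall. Once three progressions have been read among the first 14 patients, the condition is met whatever happens to the rest. Each result is available patient by patient, from the neck CT at the end of that patient's Step One. A single scheduled look after 14 completers, with accrual continuing, therefore postpones the review without improving the trigger.

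At stake are the patients who enrol between the reading of the third progression and the 14-patient look. Each spends eight weeks on a single agent before potentially curative treatment, after the trial's own warning condition has been met. In a trial of 24 patients, a few such patients are a noticeable share.

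**Working it through.** **The plan's own figure.** There is none to reproduce. Section 14.7 gives no operating characteristics for the three-progression rule, and the documents state no expected progression rate. The true rate p is therefore assumed at 10%, 20% and 30%.

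**Inputs from the plan.** Threshold 3 and window 14 patients (section 14.7); Step One 56 days (section 5.0). Applying the threshold to the first 14 is a reading of the look sentence and the trigger sentence together. Patients are taken as independent and read in order of enrolment.

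**Step 1: probability that the trigger fires.** With X ~ Binomial(14, p), P(X ≥ 3) = 1 − P(0) − P(1) − P(2).

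- p = 10%: 1 − 0.2288 − 0.3559 − 0.2570 = 0.158
- p = 20%: 1 − 0.0440 − 0.1539 − 0.2501 = 0.552
- p = 30%: 1 − 0.0068 − 0.0407 − 0.1134 = 0.839

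These hold for a running count and for a single look, because at least three among 14 is the same event as the third occurring at or before patient 14.

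**Step 2: when the third progression occurs.** Let K be the position of the third progression. P(K = k) = C(k−1, 2) p³ (1−p)^(k−3), for k = 3 to 14. Since k·C(k−1, 2) = 3·C(k, 3), the sum of k·P(K = k) up to 14 equals (3/p) × P(Binomial(15, p) ≥ 4). Dividing by the trigger probability gives the mean position when the rule fires.

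- p = 10%: (3/0.1) × 0.05556 = 1.667; 1.667 / 0.1584 = 10.5
- p = 20%: (3/0.2) × 0.3518 = 5.278; 5.278 / 0.5519 = 9.6
- p = 30%: (3/0.3) × 0.7031 = 7.031; 7.031 / 0.8392 = 8.4

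**Step 3: size of the gap.** The gap when the rule fires is 14 minus the mean position. Multiplying by the trigger probability averages it over all trials, including those that never trigger.

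| Assumed progression rate | Trigger probability, either timing | Mean position of third progression, if triggered | Patients before the 14th, if triggered | Same, averaged over all trials |
|---|---|---|---|---|
| 10% | 16% | 10.5 | 3.5 | 0.6 |
| 20% | 55% | 9.6 | 4.4 | 2.5 |
| 30% | 84% | 8.4 | 5.6 | 4.7 |

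**Step 4: does the eight-week reading lag remove the gap?** Patients already in Step One when the third progression is read are there under either timing, so enrolment at the moment of action was simulated. The simulation used a 56-day lag, a cap of 24 patients and accrual of one patient per month (an assumption; the documents give no accrual rate). Mean enrolment among triggering trials, running count against single look:

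- p = 10%: 12.3 against 15.9
- p = 20%: 11.4 against 15.8
- p = 30%: 10.1 against 15.8

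The difference stays at about 3.5, 4.4 and 5.7. It is nearly the same at 0.5 and 2 patients per month, because the lag shifts both timings alike.

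**The case against.** **The trigger may already run.** Its sentence has no date, so it can be read as acting whenever the third progression occurs, with the 14-patient look as a separate summary for abstract presentation. This cannot be excluded. The other reading is better supported: the look sentence comes first, and the authors wrote of a continuous method for delays but not for progression. If a running check was meant, one clarifying sentence says so.

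**The trigger may not exist.** If the closing sentence governs, there is nothing to time. This stands in full: the contradiction must be resolved first, and the timing point applies only if the trigger survives.

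**Waiting does add information.** A reader might infer that the third progression fixes the outcome. The documents do not support that, because the consequence is a review with three possible results. Three progressions in 5 patients and three in 14 are different evidence. Among triggering trials, the count at 14 exceeds three in 55% of cases at a 20% rate (1 − 0.2501/0.5519) and in 77% at 30% (1 − 0.1943/0.8392). Later data inform the decision, but not the trigger.

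**Other oversight exists.** Section 11.0 requires review of all patient data at least every six months and a semi-annual report that covers early stopping rules; section 5.7 allows the centre to close the study. These soften the gap, but neither sets an action threshold for progression.

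**The eight weeks are the planned design.** Every patient receives Step One, and section 5.7 sends patients who progress after it on to Step Two. This is so; the point concerns only enrolment after the warning condition is met.

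**Conclusion.** The point holds in a limited form. Section 14.7 schedules the progression check once, after 14 patients have completed Step One, while accrual continues, and its sentences on the trigger and on the stopping rule contradict each other. If the trigger is kept, a running count fires with exactly the same probability and, when it fires, does so on average about 3.5 to 5.6 patients earlier at progression rates of 10% to 30% (0.6 to 4.7 averaged over all trials). These figures rest on assumed rates and on applying the count to the first 14 patients.

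A reader might take the 3.5 to 5.6 as patients certain to be spared. They are not: they are spared only if the review closes or changes the trial. If it continues as planned, they are enrolled anyway.

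A reader might also infer that the delay table has the same fault because it starts at patient 4. It does not: that rule is already continuous, and two delays among the first two or three patients already guarantee its first threshold.

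**What to change.** In section 14.7, first settle whether the three-progression trigger applies. If it does:

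1. State that progressions are kept as a running count over the first 14 patients, updated as each end-of-Step-One CT is read.
2. State that the accrual pause and the review (amend, close or continue) start when the third progression is read.
3. Keep the scheduled 14-patient summary.
4. Reconcile with this the sentence that sets the stopping rule aside and the sentence that keeps accrual open during the interim analysis.

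The cost is a few sentences. No extra scans or data are needed, and the trigger probability does not change. The downside is that the review may start with fewer patients' data, and accrual may pause earlier than under the single look. The delay table needs no change.

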### **5.3.2 Step One Assessments**

1. Between Cycle 2 post-treatment Day 21 – Day 27, tumor response assessment will be performed by radiologic assessment with CT neck (with IV contrast).
2. Between Cycle 2 Days 18-22, office FOE or OR mDLx to document the size and extent of the PTS along with biopsy of the PTS. Core or excisional biopsies of the involved neck nodes is an alternative approach to obtain tumor tissue.
3. Between Cycle 2 Days 18-22 primary disease site photographs.
4. Clinical examination Cycle 1 Days 1, 15, and 22, and Cycle 2 Day 1 and 22.
5. CBC Days 1, 8, 15, and 22 of each cycle.
6. EKG Cycle 2: Day 1.
7. AE assessments weekly for two cycles.
8. Study Lab collection of 3 green top tubes for PBMC at C1D22 and C2D22.

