## **5.7 Duration of Therapy**

If at any time the constraints of this protocol are considered to be detrimental to the patient's health and/or the patient no longer wishes to continue protocol therapy, the

protocol therapy should be discontinued and the reason(s) for discontinuation documented in the case report forms.

In the absence of treatment delays due to adverse events, treatment may continue for 2 cycles of neoadjuvant palbociclib, 6 weeks of CRT, and 6 cycles of adjuvant palbociclib or until one of the following criteria applies:

- Documented and confirmed disease progression after Step 2. Patients with disease progression after Step 1 should proceed to Step 2.
- Death
- Adverse event(s) that, in the judgment of the investigator, may cause severe or permanent harm or which rule out continuation of study drug
- General or specific changes in the patient's condition render the patient unable to receive further treatment in the judgment of the investigator
- Suspected pregnancy
- Serious non-compliance with the study protocol
- Lost to follow-up
- Patient withdraws consent
- Investigator removes the patient from study
- The Siteman Cancer Center decides to close the study

Patients who prematurely discontinue treatment for any reason will be followed as indicated in the study calendar.

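### The interim progression count in Section 14.7 cannot register a patient who dies of disease, or stops Step One for clinical progression, without the completion CT

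*Combined protocol and SAP*

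**What the plan says.** Section 14.7 places the look as follows: "An interim efficacy assessment will be performed after the first 14 patients are enrolled and have completed step one". It then gives an express definition of progression for this purpose: "disease progression on CT scan of the neck (assessed by RECIST criteria) occurring at the completion of step one". The threshold comes in the next sentence: "The occurrence of three or more progression events during step one will be cause to stop trial accrual", so that the trial can be amended, closed or continued. The same paragraph ends with "The stopping rule will not be considered in this interim efficacy analysis given the small sample size".

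Other sections determine who can have that CT:

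- Section 5.3.2 schedules one Step One response scan, at the end: "Between Cycle 2 post-treatment Day 21 – Day 27, tumor response assessment will be performed by radiologic assessment with CT neck".
- Section 5.7 lists progression as a reason to end treatment in these terms: "Documented and confirmed disease progression after Step 2. Patients with disease progression after Step 1 should proceed to Step 2". It also ends treatment for death and for this general reason: "General or specific changes in the patient's condition render the patient unable to receive further treatment in the judgment of the investigator".
- Section 5.4 makes a patient non-evaluable for response after stopping for an adverse event, withdrawal or early death before the end-of-Step-One assessment, if no disease assessment exists.
- Section 14.6 analyses data as observed, without imputation.
- The safety rule in Section 14.7 counts only delays in starting chemoradiation caused by adverse events at least possibly related to palbociclib.

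**The concern.** The look is meant to warn if single-agent palbociclib lets tumours grow before chemoradiation that Section 14.7 itself calls potentially curative. The event is tied to one scan at the end of a period of two 28-day cycles. The worst outcomes in that period, death from disease and deterioration that ends Step One, are the ones most likely to leave no scan. Under the stated definition they do not count. They also fall outside the safety rule, because they are not palbociclib-related delays. A disease death in Step One would therefore move neither rule.

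The loss runs in one direction. Each failure without a scan makes three events harder to reach, and the progression figure that Section 14.7 plans to present at meetings would look better than the experience of the patients treated.

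**Working it through.** **Plan's own figure.** There is none to reproduce: Section 14.7 gives no operating characteristics for three events in 14.

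**Which failures count under the stated definition**

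| Step One course | Counted? |
|---|---|
| Progresses early, stays to the completion CT, CT shows RECIST progression | Yes |
| Stops early for clinical progression, no completion CT | No under the definition; the wording about events during Step One points the other way |
| Dies of disease before the CT | No; death is not named as an event in either sentence |

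**Inputs.** From Section 14.7: n = 14, threshold 3. Assumed, because the documents give neither: p, the true rate of Step One failure (progression or disease death), at 20% and 25%; and f, the share of those failures with no completion CT, at 0, 10%, one third and one half.

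**Formulas.** The text allows two readings of the set.

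- 14 completers: failures without a CT drop out and are replaced by later patients. The counted rate is p(1 − f)/(1 − pf).
- First 14 enrolled: failures without a CT stay among the 14 but do not count. The counted rate is p(1 − f).

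The chance of reaching the threshold is P(X ≥ 3), with X binomial with n = 14 and the counted rate.

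**Example.** With p = 0.25 and f = 1/3:

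- Completers: 0.25 × 0.6667 / (1 − 0.0833) = 0.1818, so P(X ≥ 3) = 48.2%.
- First 14 enrolled: 0.25 × 0.6667 = 0.1667, so P(X ≥ 3) = 42.1%.

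**Results**

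| True rate p | Set | f = 0 | f = 10% | f = 1/3 | f = 1/2 |
|---|---|---|---|---|---|
| 25% | 14 completers | 71.9% | 66.0% | 48.2% | 32.3% |
| 25% | first 14 enrolled | 71.9% | 64.1% | 42.1% | 25.1% |
| 20% | 14 completers | 55.2% | 48.9% | 32.3% | 19.8% |
| 20% | first 14 enrolled | 55.2% | 47.4% | 28.4% | 15.8% |

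The direction is the same on both readings. With f = 10% the loss is about 6 to 8 percentage points. The large losses need a large share without a CT: at p = 25% about 0.25 × 14 = 3.5 of 14 patients fail, and f = 1/2 means nearly two of them have no scan.

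**Cost of counting every failure.** At a lower true rate of 10%, the chance of a pause is 15.8% with all failures counted. With f = 10% it is 12.8% (completers) or 12.6% (first 14 enrolled).

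**The case against.** The strongest reply is that the text is less exclusive than its definition sentence suggests.

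- **Timing.** The threshold sentence counts events during Step One. That supports counting earlier progression, so early clinical progression is an internal conflict and not a settled exclusion. It does not help with death, which neither sentence names. The term progression events also takes its meaning from the definition just before it.
- **Route out of Step One.** Progression is not a listed reason to stop Step One. A reader might infer that everyone who progresses early is lost to the count. The documents do not support that: those who stay to the CT are counted, and Section 5.4 does not list stopping for progression among its reasons for non-evaluability. The general clause in Section 5.7 does allow exit on deterioration, and death ends treatment.
- **Denominator.** A reader might infer that non-completers are removed from the 14. The words "after the first 14 patients are enrolled and have completed step one" may only fix when the look takes place, and nothing says that such patients are dropped or replaced. The supported criticism is that their handling is unspecified.
- **Force of the rule.** A reader might infer that the rule is blunted however the paragraph is resolved. If the closing sentence governs, no trigger exists to blunt, and what remains is a reported count that omits failures.
- **Other oversight.** Deaths go on the Toxicity and Death Forms (Sections 12.0 and 12.1), and the safety committee receives semi-annual reports (Section 11.0). This cover is partial: Section 7.2 exempts events related to disease progression from expedited reporting, and none of it feeds the three-event count.

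**Conclusion.** The concern stands in this form. Followed as written, the Section 14.7 definition omits disease death, and clinical progression that ends Step One, when no completion CT exists. The safety rule does not fill the gap, and non-completers among the first 14 have no stated handling. The definition also conflicts with the sentence after it on timing.

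The documents fix the direction but not the size. At an assumed true rate of 20% to 25%, the chance of reaching three events drops by about 6 to 8 points if 10% of failures have no CT. At 25% it drops by 24 to 30 points if one third have none (71.9% to 48.2% or 42.1%). Whether this weakens a stopping trigger or only a reported figure depends on which of the two sentences, "The occurrence of three or more progression events during step one will be cause to stop trial accrual" or "The stopping rule will not be considered in this interim efficacy analysis given the small sample size", governs. The correction should be made because the gap affects the most serious outcomes and is cheap to close.

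**What to change.** Amend Section 14.7 to:

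1. Define the interim set as the first 14 patients who start palbociclib, with no replacement.
2. Count as an event RECIST progression on any Step One CT, clinical progression that ends Step One early, or death from disease before the Step One CT.
3. Use one timing phrase in both the definition and the threshold sentence.
4. Reconcile the sentence that makes three events a cause to stop accrual with the one that sets the stopping rule aside, and state which governs.
5. Give the chance of reaching three events over a range of true rates.

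No new data are needed. Section 5.7 already requires discontinuation reasons on the case report forms, Section 12.0 has a Death Form, and Section 12.1 records death from progression as a grade 5 event. The cost is a few sentences and a slightly higher chance of an accrual pause. By Section 14.7's own terms such a pause leads to a review whose outcomes include continuing as planned.

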### **Palbociclib Oral Solution**

For patients who are unable to swallow capsules, a PD 0332991 oral solution is available as of IRB/EC approval of Amendment 5.

For patients who develop inability to swallow capsules during the study, it is allowed to switch to the PD 0332991 oral solution.

The PD 0332991 oral solution (25 mg/mL) will be administered using an oral syringe at volumes corresponding to the dose prescribed by the investigator (125 mg dose = 5mL, 100 mg dose = 4 mL, and 75 gm dose = 3 mL). Detailed instructions for administration of the oral solution can be found in the DAI.

PD 0332991 oral solution will be administered once a day, orally or via feeding tube, for 21 days followed by 7 days off treatment in 28-day cycles. The route of administration of the oral solution (oral vs via feeding tube) will be recorded in patient's dosing diary and the study CRF.

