#### **14.4 Study Population**

Twenty-four eligible patients with p16INK4a negative/HPV-unrelated OPSCC, larynx SCC, hypopharynx SCC, and oral cavity SCC will be enrolled into the trial to receive 2 months of neoadjuvant palbociclib monotherapy at Step One, 6-7 weeks CRT (either cisplatin or cetuximab) at Step Two, and 6 months of adjuvant palbociclib at Step Three. The sampling method is non-random. Patients with excellent performance status and adequate vital organ function at enrollment will be assigned to the cisplatin cohort. Patients with reduced performance status and/or vital organ function will be assigned to the cetuximab cohort.

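### The continuous boundary for palbociclib-related delay of chemoradiation ends at patient 14, so patients 15 to 24 have no pre-specified trial-level delay threshold

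*Combined protocol and SAP*

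**What the plan says.** Section 14.7 defines the trial's safety rule. "The safety endpoint of interest is delays in starting potentially curative chemoradiation therapy", with an event being "failure to start chemoradiation within three weeks of cycle 2 day 28 (of Step One) due to adverse events" that are at least possibly related to palbociclib. The scope is limited: "A safety assessment will be performed for the first 14 patients enrolled using a continuous method". When a threshold is met, "Trial accrual should be stopped to assess if the trial should be amended, closed, or continued as planned".

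The printed thresholds are 2 delays in the first 4, 5 or 6 patients; 3 in 7, 8 or 9; 4 in 10 to 13; and 5 in 14. There is no row after 14.

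Section 14.4 plans "Twenty-four eligible patients". Section 14.1 gives all of them two 28-day cycles of neoadjuvant palbociclib. Sections 5.3.3 and 5.3.4 have Step Two begin the day after Cycle 2 Day 28, whichever cohort the patient is in.

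After patient 14, the following oversight remains:
- Section 11.0: ongoing monitoring of serious toxicities, investigator review of all data at least every six months, and a semi-annual report to the monitoring committee.
- Section 6.1: withholding, reduction and discontinuation of palbociclib for toxicity in the individual patient.
- Section 5.7: discontinuation of protocol therapy.

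None of these contains a threshold for chemoradiation delay. The semi-annual report must cover early stopping rules, but that creates no new one.

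**The concern.** The protocol itself singles out delay of potentially curative treatment as the harm to watch for. The drug, the schedule and the hand-over to chemoradiation are the same for patient 15 as for patient 14, yet the rule stops counting. If the boundary has not been crossed by patient 14, no later number of delays triggers a pause. The protocol states neither why monitoring ends there nor what delay rate the table is meant to detect, so a reader cannot tell a deliberate lead-in from an oversight.

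**Working it through.** **Inputs.** Boundary, endpoint and action from Section 14.7; N = 24 from Section 14.4. The protocol states no acceptable delay rate or error target for this table, so there is no published operating characteristic to reproduce. Constant delay rates of 10 to 40% are assumed to show a range.

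**Coverage.** 24 − 14 = 10 patients; 10/24 = 41.7%.

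**Printed table.** Let q(n, x) be the probability of x delays in the first n patients with no threshold met so far, and p the delay rate. Then q(n, x) = (1 − p)·q(n−1, x) + p·q(n−1, x−1). After each patient with a row, the mass at or above that row's threshold is removed and counted as a pause. At p = 0.30, the mass left uncrossed after patient 14 is 0.0068, 0.0407, 0.0947, 0.1094 and 0.0325 for 0, 1, 2, 3 and 4 delays, in total 0.2841. The pause probability is 1 − 0.2841 = 0.716.

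**Extending the table.** The printed rows do not fix a unique continuation.
- *Loosest.* The lowest printed fraction is 4/13 = 30.8%. Rounding 4n/13 up to a whole number reproduces all 11 printed rows. For later patients it gives 5 in 15-16, 6 in 17-19, 7 in 20-22 and 8 in 23-24.
- *Strictest.* Bayesian rules were searched of the form: pause when the posterior probability that the delay rate exceeds a target is above a cutoff, under a beta prior. Eight distinct continuations agree with all 11 printed rows. The loosest of them equals the one above. The strictest is 5 in 15-18, 6 in 19-22 and 7 in 23-24.

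**Pause probabilities.**

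| Assumed delay rate | By patient 14, as printed | By 24, loosest | By 24, strictest |
|---|---|---|---|
| 10% | 13.1% | 13.4% | 14.0% |
| 20% | 42.8% | 45.7% | 50.0% |
| 30% | 71.6% | 77.7% | 82.7% |
| 40% | 89.6% | 94.5% | 96.7% |

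Before rounding, the 10% row reads 13.14, 13.39 and 13.97%, so the rise in unnecessary pauses is 0.25 to 0.83 points.

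**Given that patient 14 is passed without crossing.** Divide the gain by the uncrossed probability. At 30%, loosest: (0.7769 − 0.7159)/0.2841 = 0.21; strictest: (0.8271 − 0.7159)/0.2841 = 0.39. At 40% the same calculation gives 0.47 and 0.68. Under the plan as written all four are zero.

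**Enrolments avoided.** Sum (24 − n) × P(first crossing at patient n) over n = 15 to 24, treating outcomes as known at once. At 30% with the loosest extension, the crossing probabilities are 0.0097, 0.0167, 0.0063, 0.0115, 0.0046, 0.0086 and 0.0035 at patients 15, 16, 18, 19, 21, 22 and 24. The sum is 9(0.0097) + 8(0.0167) + 6(0.0063) + 5(0.0115) + 3(0.0046) + 2(0.0086) + 0(0.0035) = 0.35. Across 10, 20, 30 and 40% the results are 0.02, 0.18, 0.35 and 0.28 patients for the loosest extension.

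**Lag.** The endpoint may not be known until 56 days of Step One plus 21 days = 77 days after a patient starts. The real saving is therefore smaller than these figures.

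**What can pass the printed table.** Four delays in the first 14 patients escape only if the fourth delay is patient 14 itself, because 4 in 13 already triggers. As an extreme bound, that path followed by ten further delays would leave 4 + 10 = 14 of 24 patients (58%) delayed without a trigger.

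**The case against.** The strongest reply is that the rule is a lead-in. The interim efficacy look in the same section uses the same 14 patients, a high constant delay rate would probably be caught by then, and the extension gains at most about 6 points with the loosest thresholds (about 11 with the strictest), for a fraction of one enrolment avoided. A crossing at patient 24 stops nothing. All of this stands and limits the importance of the point. It does not remove the gap, because the protocol nowhere says that a lead-in was intended.

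Three stronger readings are tempting, and the documents do not support them.

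- A reader might infer that patients 15 to 24 are unprotected. They are not: Sections 5.7, 6.1 and 11.0 still apply to them. What is missing is a trial-level delay threshold.
- A reader might infer that later patients differ, because the "oral solution is available as of IRB/EC approval of Amendment 5". That sentence concerns a formulation. The eligibility criteria contain no swallowing requirement, enrolment at the time of Amendment 5 is not given, and Section 8.1 reports the solution as bioequivalent to the capsule. Nothing links it to more delay.
- A reader might posit a sharp rise in the delay rate after patient 14, which would make the gain look much larger. No passage supports such a shift.

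**Conclusion.** The point holds as a matter of coverage: 10 of 24 patients (42%) receive the same Step One treatment with no pre-specified delay boundary and no stated reason. Its practical weight is modest. At a constant delay rate the extension adds about 0.25 to 0.8 points of pause probability at 10%, 3 to 7 at 20%, 6 to 11 at 30% and 5 to 7 at 40%. It matters most where the rate is high and the first 14 patients happened not to cross: the extended table would then still pause 21-39% of trials at a 30% rate and 47-68% at 40%.

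These figures assume independent patients, a constant delay rate, outcomes known without lag, and extensions consistent with the printed rows. The delay rates are assumptions, since the protocol names none. This is an inexpensive improvement to the plan; it is not a defect that undermines the trial.

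**What to change.** In Section 14.7, apply the continuous assessment to all patients instead of the first 14, and extend the table to 24 on the same basis as the printed rows. State the delay rate the table targets and the criterion behind it. The printed rows alone leave a range, from 5 in 15-16, 6 in 17-19, 7 in 20-22 and 8 in 23-24 to 5 in 15-18, 6 in 19-22 and 7 in 23-24, so the sponsor should derive the new rows from the stated target. If a lead-in is intended, the section should say so and give the reason.

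The cost is a few table rows and a sentence. The Step 1 and Step 2 Treatment Forms and the Toxicity Form in Section 12.0 are already collected for every patient. The downside is the small rise in unnecessary pauses shown above, and a pause only prompts a review of whether to amend, close or continue.
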